To measure the energy expenditure using indirect calorimetry in mechanically ventilated children admitted to the intensive care unit before, during and after fever.

HYPOTHESIS

Null hypothesis: Fever will be associated with <10% difference of baseline energy expenditure per 1°C change in temperature in critically-ill children ventilated on the intensive care unit

Alternative hypothesis: Fever will be associated with a >10% difference of baseline energy expenditure per 1°C change in temperature

STUDY DESIGN

Prospective observational cohort study

STUDY POPULATION

Children admitted to the paediatric intensive care unit at Great Ormond Street Hospital with suspected infection, following trauma or major surgery, who are likely to develop a fever.

ELIGIBILITY CRITERIA

Inclusion criteria:

- Children >10kg (The MedGraphic Ultima CCM calorimeter has been used safely in children as low as 10kg)
- Children with suspected infection, following trauma, or post-major surgery

Exclusion criteria:

- Children post brain injury
- Children with refractory status epilepticus
- Children post cardiac arrest
- Children post cardiac bypass
- Children with cardiac arrhythmias
- Children not invasively ventilated
- Children with a greater than 5% leak around their endotracheal tube
- Children with a fraction of inspired oxygen (FiO_2)>0.60
- Children above 16 years of age

STUDY OUTCOMES

Primary outcome: Change in energy expenditure per degree Centigrade change in temperature

Secondary outcome: Change in oxygen extraction ratio (ratio of oxygen consumption to oxygen delivery) per degree Centigrade change in temperature using oxygen delivery data from the Lidco Rapid (LIDCO Ltd, UK) cardiac output monitor if in place.

STUDY PROCEDURES

Screening and Recruitment

- All patients will be screened each morning (Mon-Fri) by the PI for weight, ventilation status and likelihood of developing a fever (The PI is part of the wider clinical team)
- The PI will ask the clinical team on call if calorimetry is suitable for the identified patient/s
- If the clinical team feel this is appropriate, the PI will ask consent of the parents to undertake indirect calorimetry

Study procedure

1. Once consented, calorimetric measurement will be undertaken using the MedGraphic Ultima CCX, Minnesota, USA). This will be done in the following steps:
 - a. Assess the patient for stability:

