 - i. no change in inotropes (dopamine, adrenaline, noradrenaline, vasopressin, milrinone, dobutamine) in previous hour
 - ii. no change in ventilator settings including FiO₂ in the previous hour
 - iii. FiO₂ <0.6
 - iv. tidal volume ventilation >60ml (ideally greater than 100ml)
 - v. air leak around endotracheal tube (ETT)<5%
 - vi. no increases in sedation in past hour
 - vii. no major stimulatory events (physiotherapy, turning, suction) in the previous hour
 - b. Record demographic data, ventilator settings and measurements, calorie intake, heart rate, blood pressure, cardiac index (if monitored), drug infusion rates, use of paralysis, COMFORT or sedation score, temperature
 - c. If the patient is stable, then start measurement of energy expenditure (calibrate prior to measurement, attach gas sampler to end of ETT to ventilator end of capnograph/flow sensor).
 - d. Stop measurement immediately if any deterioration in ventilation with measurement
 - e. After 30 minutes (or sooner if steady state is reached i.e. 5 consecutive minutes of less than 10% variation in O₂ and CO₂ concentrations) stop measurement
2. If patient develops temperature >38°C (axillary or central measurement) within the next 4 hours (or longer only if all variables are the same as baseline), repeat step 4 a-c prior to anti-pyretic administration (with half hourly data collection). The calorimeter will be left on the patient for continuous data collection until the temperature falls below 38°C.
3. If continuous measurement is not possible because of clinical needs (nursing or medical request, need for suctioning, patient instability), a 3rd measurement will be taken when the temperature is below 38°C

If the patient is febrile at screening, measurement will start at step 2

Patient safety

The calorimeter fits in to the ventilator circuit. This requires very brief disconnection of the circuit to attach the sampling connector. Disconnection of this nature is routine practice in the intensive care unit (for example during suctioning) and is well tolerated.

The calorimeter samples air from the ventilator circuit at a constant rate of 100ml/min. This may affect ventilation in small children. The Medgraphic Ultima CCM is licensed for use for patients with tidal volumes of 100ml or more. This will usually equate to children around 15kg. However our collaborators in Addenbrooke's Hospital, Cambridge (Dr [name]) have used the Medgraphic Ultima CCM safely in children down to 10kg.

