During measurement we will monitor the child's respiratory rate, oxygen saturation levels and end tidal CO₂. If any of these values change significantly, as judged by the bedside nurse or the PI, calorimetry will be discontinued.

Data collection

Data will be collected for

- Demographic data (ID, weight, height, age, sex, diagnosis)
- Inspired and expired O₂ and CO₂; VO₂ and VCO₂; Respiratory Quotient; Energy expenditure (as measured and displayed by the MedGraphics Ultima CCM calorimeter)
- Physiological variables (heart rate, blood pressure)
- IF CARDIAC OUTPUT MONITOR IN PLACE: stroke volume and cardiac index (as measured by Lidco Rapid, LIDCO Ltd, UK) and latest haemoglobin
- Inotrope infusion doses
- COMFORT or sedation score as recorded
- Paralysis (yes/no)
- Temperature
- Nutritional intake in last 24 hours or since admission

Data apart from demographic data will be collected at the start of each recording and hourly if continuous recording

If cardiac monitoring is in place, continuous data (as recorded by the Lidco Rapid) will be used to calculate oxygen delivery.

STATISTICAL ANALYSIS

Sample size: Not enough data exists to ascertain the standard deviation of energy expenditure using the Medgraphics Ultima CCM calorimeter in critically ill children over the time period to be measured. However a standard deviation of 10% has been observed in critically ill children by groups who have measured energy expenditure in large numbers of children (personal communication from Dr [name], Imperial College, London). Based on this, for a 10% effect size, with a one-tailed α of 0.05 and (1- β) of 0.8, a sample size of 10 children would be needed, provided a 1°C of temperature is seen. An analysis of temperature change following over 5000 doses of paracetamol in febrile children suggested a mean reduction of temperature by 0.7°C. Based on this therefore we will need $10 \times 1/0.7 = 15$ patients

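### Steady state is defined on O₂ and CO₂ concentrations rather than VO₂ and VCO₂, and only for the first reading, so a reading can stop early without energy expenditure being shown to be stable

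*Combined protocol and SAP*

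**What the plan says.** The primary outcome (Study outcomes) is "Change in energy expenditure per degree Centigrade change in temperature", and the alternative hypothesis is that "Fever will be associated with a >10% difference of baseline energy expenditure per 1°C change in temperature".

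Under Study procedure, step 1e ends a reading as follows: "After 30 minutes (or sooner if steady state is reached", with steady state defined as "5 consecutive minutes of less than 10% variation in O₂ and CO₂ concentrations". It does not say whether the concentrations are inspired, expired or the difference between them, whether 10% is a total range or a plus-or-minus figure, or what happens to a reading that reaches 30 minutes without meeting the rule. No minimum run-in is given.

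The Data collection section lists what the calorimeter measures and displays: "Inspired and expired O₂ and CO₂; VO₂ and VCO₂; Respiratory Quotient; Energy expenditure". Concentrations are therefore named separately from VO₂ and VCO₂.

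Step 1a requires stability over the hour before a reading, including "no change in ventilator settings including FiO₂ in the previous hour". Under Patient safety, the protocol adds: "During measurement we will monitor the child's respiratory rate, oxygen saturation levels and end tidal CO₂", with calorimetry discontinued if the nurse or investigator judges a change significant.

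For the fever reading, step 2 says "repeat step 4 a-c prior to anti-pyretic administration" and then leaves the calorimeter on until the temperature is below 38°C. There are only three numbered steps, so the reference is presumably to step 1, and 1e is not among the parts repeated. Step 3 adds a third reading when continuous recording is not possible, without a stopping criterion. Children febrile at screening begin at step 2.

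**The concern.** VO₂ is minute ventilation multiplied by a small difference between inspired and expired O₂. A tolerance set as a percentage of the O₂ concentration is therefore much looser when expressed as a percentage of VO₂, and it becomes looser as FiO₂ rises. A rule on concentrations also places no limit on minute ventilation, the other factor in both VO₂ and VCO₂.

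An early-stopped reading may thus count as steady although EE has not been shown to be so. The effect under test is 10% of baseline per 1°C, and the comparison is within-patient with a target of at least 15 children, so avoidable reading error could matter. The rule is also written for the first reading only, so the two sides of a paired comparison need not meet the same standard.

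**Working it through.** **Inputs from the protocol.** 10% tolerance over 5 minutes (step 1e); FiO₂ below 0.6 (step 1a); SD of EE 10%, one-tailed α 0.05, temperature change 0.7°C, N = 15 (Sample size).

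**Assumptions not in the protocol.** The concentration is expired O₂; 10% is the total width of the permitted range; the inspired-expired gap is 3 to 5 percentage points; for steps 2 and 4, the Weir weights (3.941 for VO₂, 1.106 for VCO₂) and a respiratory quotient (RQ) of 0.85; for step 4, the Haldane correction and mixed expired CO₂ of 2-4%.

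**1. What the O₂ limb alone tolerates.** Band as a share of the gap = 0.10 × (FiO₂ − gap) / gap.

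| FiO₂ | gap 0.05 | gap 0.03 |
|---|---|---|
| 0.21 | 0.10 × 0.16 / 0.05 = 32% | 0.10 × 0.18 / 0.03 = 60% |
| 0.40 | 0.10 × 0.35 / 0.05 = 70% | 0.10 × 0.37 / 0.03 = 123% |

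A band wider than the gap would allow an apparent VO₂ of zero or below. These figures describe how little the limb constrains VO₂; they do not estimate the error in a reading.

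**2. What the CO₂ limb adds at constant ventilation.** VCO₂ = VE × FeCO₂, where VE is minute ventilation and FeCO₂ is expired CO₂, so a real 30% rise in EE at fixed RQ raises expired CO₂ by 30% and fails the rule. With expired CO₂ held within ±5% and RQ fixed, EE is held within ±5%. If RQ moves between 0.8 and 0.9, EE relative to RQ 0.85 runs from 0.95 × (3.941/0.9 + 1.106) / (3.941/0.85 + 1.106) = 0.91 to 1.05 × (3.941/0.8 + 1.106) / (3.941/0.85 + 1.106) = 1.10, or about ±10%. Most real swings are therefore caught.

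**3. Ventilation and metabolism moving together.** VO₂ and VCO₂ are each VE times a function of concentrations. If VE and metabolism both rise by 10%, 20% or 30%, both concentrations stay flat and EE rises by 10%, 20% or 30%. Neither limb responds.

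**4. O₂ error or FiO₂ drift without a CO₂ change.** With the Haldane correction, VO₂/VE = FiO₂ × (1 − FeO₂ − FeCO₂)/(1 − FiO₂) − FeO₂, so an error in expired O₂ (FeO₂) is multiplied by 1/(1 − FiO₂). At FiO₂ 0.40 and expired CO₂ 3%, FeO₂ = 0.3668 and VO₂/VE = 0.03/0.85 = 0.0353. A 1% error in FeO₂ is 0.003668; 0.003668 / 0.6 / 0.0353 = 17% of VO₂. VO₂ carries 81% of EE here, so EE moves 14%. Over expired CO₂ 2-4% the range is 22% to 10%. A 1% O₂ error is well inside the 10% limit.

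**5. Which readings the rule covers.** Baseline: step 1e applies. Fever: only parts a to c are repeated, with continuous recording. Third reading: no criterion. A child febrile at screening has no reading to which 1e is stated to apply.

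**6. What extra SD would cost (illustration only).** The plan's step from 10 to 15 children is 10/0.7 = 14.3, rounded up to 15. For a paired t-test against zero with n = 15 and a change of 7% (10% × 0.7), the noncentrality is √15 × 7/SD and the one-sided critical value is t(0.95, 14 df) = 1.761.

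| SD of change | noncentrality | power |
|---|---|---|
| 10% | 2.71 | 82% |
| 12% | 2.26 | 69% |
| 15% | 1.81 | 53% |

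Nothing in the protocol links the concentration rule to an SD of 12% or 15%.

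**The case against.** The strongest reply is that both limbs must hold. A reader might infer from the O₂ band that the rule is met almost at once and that widely swinging readings enter the analysis. The documents do not support that: at constant ventilation the CO₂ limb blocks most real metabolic swings, and nothing shows how often the remaining cases arise.

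The safeguards also count. The hour of stability beforehand and the bedside watch on respiratory rate, saturation and end-tidal CO₂ narrow the ventilation route, and in a paralysed child on fixed settings it is largely closed. RQ is displayed and recorded, so grossly implausible O₂ values should be visible, although no rejection rule is given. None of this tests VO₂ or EE stability.

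The wording may be shorthand. If the inspired-expired difference is meant, VO₂ is held to about 10% at constant ventilation, with ventilation still unrestricted. If VO₂ and VCO₂ are meant, the text needs the same correction, because Data collection names them separately.

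A reader might also infer that the extra noise lies outside the 10% SD used for the sample size, or that dividing by 0.7°C costs further power. Neither can be shown. The SD is a personal communication with no account of how those readings were taken. A constant divisor scales signal and noise alike, and the 7% effect already uses 0.7.

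**Conclusion.** The point holds as a defect of specification. The early-stopping rule tests concentrations when the outcome depends on VO₂ and VCO₂, and no criterion is stated for the later readings. The O₂ limb alone tolerates 32-60% of the inspired-expired gap at FiO₂ 0.21 and 70-123% at 0.40. That is an upper bound for the limb on this simple ratio, resting on the expired-O₂ reading and the assumed gap. The weaknesses that survive the CO₂ limb are ventilation and metabolism changing together, O₂ error or FiO₂ drift, and unequal standards across paired readings. The effect on the SD and on power cannot be derived from the documents. The change is worth making because it is specific and nearly free, not because a loss of power has been demonstrated.

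**What to change.** - **Step 1e:** define steady state as 5 consecutive minutes in which VO₂ and VCO₂ each vary by less than 10%, and say how variation is calculated.
- **Steps 2 and 3:** apply the same criterion to every reading, or segment of continuous recording, used in the analysis, and correct the cross-reference to step 4.
- **Readings that reach 30 minutes without meeting it:** flag them, and repeat the primary analysis without them as a sensitivity analysis.

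The cost is a few lines across three steps and one added analysis. The calorimeter already displays both quantities and the sample size is unchanged. The downside is that some readings will run nearer to 30 minutes and a few will be flagged.

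### A child febrile at screening whose continuous recording is uninterrupted has no planned steady-state afebrile measurement, only a reading at the 38°C crossing

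*Combined protocol and SAP*

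**What the plan says.** Four provisions under Study procedure decide which readings a child contributes.

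- Step 1 takes a baseline reading, with stability conditions (1a) and an end rule (1e): stop at 30 minutes, or sooner once gas concentrations have varied by less than 10% over five minutes in a row.
- Step 2 applies "If patient develops temperature >38°C (axillary or central measurement) within the next 4 hours". It repeats items a-c, "prior to anti-pyretic administration (with half hourly data collection"), and then: "The calorimeter will be left on the patient for continuous data collection until the temperature falls below 38°C".
- Step 3 is conditional: "If continuous measurement is not possible because of clinical needs", then "a 3rd measurement will be taken when the temperature is below 38°C".
- A closing line adds: "If the patient is febrile at screening, measurement will start at step 2".

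The Study Objectives section asks for energy expenditure "in mechanically ventilated children admitted to the intensive care unit before, during and after fever". The Statistical Analysis section sets a target of at least 15 children who have both a febrile and a non-febrile reading. It describes the full before, during and after sequence as the ideal. The primary comparison is a paired t-test of the two readings divided by the temperature change. The Data collection section gives a different interval from step 2: "Data apart from demographic data will be collected at the start of each recording and hourly if continuous recording".

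**The concern.** The three rules combine badly for one group. A child febrile at screening has no step 1 baseline, so the non-febrile half of the pair must come after the fever. If continuous recording succeeds, it ends once temperature is below 38°C, and step 3 is not triggered. What remains is a value at the threshold. Step 2 carries over items a-c only, so the end rule in 1e is not applied to that value, and no period below 38°C is asked for.

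Two things are at stake for these children. First, a value taken while temperature is falling need not equal the energy expenditure after it has settled; the documents give no basis for the size or direction of the difference. Second, the primary outcome is a change per degree, so a small temperature contrast in the denominator makes the estimate imprecise. The sample size rests on a 0.7°C contrast, taken from falls after paracetamol with no cut-off at 38°C. The step 2 stopping rule can cut the observed contrast short of that. A missing afebrile reading usually cannot be recovered later.

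**Working it through.** **Readings by path, followed as written**

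| Entry | Continuous recording | Before | During | Below 38°C |
|---|---|---|---|---|
| Step 1 | uninterrupted | yes | yes | threshold value only |
| Step 1 | not possible | yes | yes | separate step 3 reading |
| Step 2 (febrile at screening) | uninterrupted | no | yes | threshold value only |
| Step 2 (febrile at screening) | not possible | no | yes | separate step 3 reading |

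Only the third row depends on the threshold value for its pair. No other section plans an afebrile reading for that child.

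**The plan's own figure.** Inputs from the sample size paragraph: SD 10%, effect 10% per 1°C, one-tailed α 0.05, power 0.8, assumed contrast 0.7°C. I read the 10% as the SD of the within-child difference, which the document does not say. The standardised effect at 1°C is 10/10 = 1. With a paired t-test (noncentral t), one-sided 0.05 needs 8 children and two-sided 0.05 needs 10 (power 0.80), so the stated 10 is adequate on this reading. Then 10/0.7 = 14.3, rounded up to 15, as stated. (Whether 1/0.7 is the right scaling is a separate matter and is not relied on here.)

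**Precision of one child's per-degree estimate.** The estimate is the difference in energy expenditure divided by ΔT, so its SD is 10%/ΔT and its variance relative to the planned contrast is (0.7/ΔT)². Febrile temperatures are assumed, since none is given. If the last value is at exactly 38.0°C:

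- 38.7°C: ΔT = 0.7, ratio 1.0
- 38.5°C: ΔT = 0.5, ratio (0.7/0.5)² = 1.96
- 38.3°C: ΔT = 0.3, ratio (0.7/0.3)² = 5.4

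If temperature is checked only at intervals, the first value below 38°C may be lower. For an assumed last value of 37.8°C:

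- 38.5°C: ΔT = 0.7, ratio 1.0
- 38.3°C: ΔT = 0.5, ratio 1.96

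**Outer bound on power.** If all 15 children had the same contrast (SD 10%, true effect 10% per °C, one-sided 0.05), power against no change would be 0.82 at 0.7°C, 0.58 at 0.5°C and 0.30 at 0.3°C. Only some children follow the affected path, so the real loss would be smaller.

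**If threshold values are not accepted.** Let f be the share of recruits on the affected path (assumed; no figure is given). Recruitment needed for 15 pairs is 15/(1 - f), rounded up:

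- f = 0.10: 17
- f = 0.25: 20
- f = 0.50: 30

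**The case against.** The strongest reply is that step 3 is a substitute. Steps 2 and 3 use the same 38°C threshold, so the authors may have meant an uninterrupted recording to run into the afebrile state, with a separate reading only where it cannot. This largely stands as an account of intent. It means a reader should not infer that affected children have no non-febrile data: fever is defined as above 38°C, and the recording ends on a value below it. What does not follow is that this value is an adequate afebrile measurement. The text does not name it as the without-fever value or apply the steady-state rule to it.

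Other parts of the reply also stand.

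- Febrile temperature minus 38°C is not a strict maximum. With half-hourly or hourly checks the contrast may be larger, as shown above.
- Children who enter at step 1 have a valid pair from the baseline and febrile readings. They lose only the after-fever reading, which the plan treats as desirable.
- It is tempting to infer that children with a step 3 reading are an unfairly selected sample with better data. The documents do not support this: step 3 sets no minimum fall, no time below 38°C and no explicit steady-state rule, so its reading may also be taken just under the threshold.
- The target of 15 already counts only children with both readings. If threshold values are rejected, the loss is therefore in recruitment yield, not in power at a fixed 15.

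**Conclusion.** The gap is real but narrow, and should be fixed. For a child febrile at screening with an uninterrupted recording, the plan provides a threshold value and no steady-state afebrile measurement. The temperature contrast is then roughly the febrile temperature minus 38°C, or somewhat more with intermittent temperature checks. Against the assumed 0.7°C, the variance of the per-degree estimate is about 2 times as large at 38.5°C and about 5.4 times at 38.3°C. Those figures assume a last value at 38.0°C and the same SD at every contrast; the febrile temperatures are illustrative.

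A reader might go further and conclude that most of the 15 pairs are compromised. The documents do not support that. They do not say how many children would be febrile at screening or how many recordings would be uninterrupted, and step 1 entrants are unaffected in their primary pair. The stated sample size is not wrong because of this point.

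**What to change.** Make the below-38°C measurement unconditional for every child who enters at step 2, and preferably for all children. After the crossing, keep the calorimeter on, or re-attach it, until a reading meets the stability and steady-state criteria of step 1a-e. This stays subject to the existing stop rules in step 1d and the monitoring under Patient safety. State that this reading is the without-fever value in the paired comparison. Record the temperature at that reading and the change achieved, without requiring a 0.7°C fall: that figure is a reported mean, and many children could miss it. Count a step 2 entrant toward the 15 only once the reading is obtained.

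In the same edit, reconcile the half-hourly and hourly collection intervals, and correct the cross-reference in step 2 to a step 4, which does not exist (items a-c sit under step 1).

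The cost is protocol wording and a short extra recording period. The extra time must be weighed against the caution under Patient safety that gas sampling at 100 ml/min may affect ventilation in small children. A few children will be lost before the reading is made, for example through instability, and will not count toward the 15. The stated sample size need not change on this account.

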Measuring the metabolic cost of fever: Indirect calorimetry in children with fever on the intensive care unit.

Protocol Version 2 (07.08.2016)

STUDY INVESTIGATORS:

Principal Investigator: [name]
PhD Student,
Respiratory, Critical Care and Anaesthesia Section,
UCL Great Ormond Street Institute of Child Health, London, UK
[contact]

Chief Investigator: [name] [name]
[name] Care Medicine
Respiratory, Critical Care and Anaesthesia Section,
UCL Great Ormond Street Institute of Child Health, London UK
[contact]

INTRODUCTION

Fever is a common immune response in children with infection or inflammation. While fever may potentiate the immune system to fight the pathogenic stimulus, energy is required to generate the raised temperature. This may be scarce in critical illness, particularly in children. We do not know how much energy is used in generating fever by children in the intensive care unit. This study aims to measure energy expenditure in children during and before/after they have a fever. We aim to do this using indirect calorimetry in at least 15 children, who are invasively ventilated on the intensive care unit. We will then calculate the average increase in energy expenditure required per 1°C rise in temperature in this population. If fever does not require a significant increase in energy expenditure in children on the intensive care unit, then treatment of fever may not have any benefits. If fever does require an increase in energy expenditure, this may counter the immunological benefits that fever confers. In such a case a randomised controlled trial comparing treatment and non-treatment of fever would be required.

BACKGROUND

Fever is an innate immune response to danger. Stimuli such as pathogens or tissue damage lead to a cascade of cytokine signals, including the release of pro-inflammatory cytokines such as TNF- α , IL-6 and IL-1. Many of these pro-inflammatory cytokines act upon the thermoregulatory centre of the hypothalamus via the release of prostaglandins, to increase the body's temperature set-point. The body responds by both reducing heat loss and increasing heat production to raise the body temperature^{1,2}.

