However it is likely that our sample will have several confounders which will need to be taken into account by multi-variable analysis. Therefore we will aim to recruit at least 15 children with measurements with and without fever (ideally before-during and after fever), but will try and recruit as many children as possible over the 12 month study period. Approximately 300 patients admitted to PICU at Great Ormond Street Hospital per year are above 10kg. Of these, approximately 75-100 patients are electively admitted, 30 post-major surgery (mostly spinal surgery). 30% of children post spinal surgery develop a fever in the first 24 hours. In addition the remaining 200 children are admitted as an emergency. 80% of children admitted as an emergency are treated for a suspected infection, the remainder post trauma. Again 30-50% of children admitted with an infection or trauma develop a fever within the first 24 hours. Therefore each year approximately 75-80 patients will be >10kg, ventilated, and will develop a fever within the first 24 hours of admission, with a proportion developing fever later on in admission (e.g. from nosocomial infections).

Statistical analysis: Uni-variable analysis using paired t-tests will be undertaken by comparing the energy expenditure with and without fever, divided by the change in temperature. Multi-variable analysis using a multi-level regression model will be used using

- Change in energy expenditure as the outcome variable
- Patient ID as the random effect variable
- Change in temperature, COMFORT score, vasoactive inotrope score, heart rate, blood pressure, and paralysis as a binary variable as fixed effect variables

If cardiac output monitoring is in place, then the oxygen extraction can be calculated as VO_2/DO_2 , where,

$DO_2 = \{cardiac\ index \times ((oxygen\ saturation\ of\ haemoglobin \times haemoglobin\ concentration) + 0.0031 \times partial\ pressure\ of\ oxygen)\}$

and VO_2 is measured from the calorimeter

ETHICAL CONSIDERATIONS

The study will be conducted in accordance to Good Clinical Practice principles and the principles of the Declaration of Helsinki.

Informed consent will be sought from parents/guardians with parental responsibility prior to measurement. Consent forms will be stored in the Great Ormond Street Critical Care Research Office securely.

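### Before-to-fever and fever-to-after pairs enter one comparison without elapsed time or order, so drift in energy expenditure is confounded with temperature whenever pair types or gaps are unbalanced

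*Combined protocol and SAP*

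**What the plan says.** Under Study procedure, step 2 takes the febrile reading within four hours of the first one; a longer gap is allowed only if all variables still match baseline. The calorimeter then stays on until the temperature falls below 38°C. Where that is not possible, step 3 says that "a 3rd measurement will be taken when the temperature is below 38°C", with no limit on when. The section closes with: "If the patient is febrile at screening, measurement will start at step 2". Those children have no pre-fever reading.

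Under Sample size, any child with a febrile and a non-febrile measurement counts toward the target of 15. Having all three phases is described only as "ideally before-during and after fever".

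Under Statistical analysis, the paired t-test works by "comparing the energy expenditure with and without fever, divided by the change in temperature". The multi-level model has change in EE as outcome and patient as random effect. Its fixed effects are change in temperature, COMFORT score, vasoactive inotrope score, heart rate, blood pressure and paralysis. No term represents elapsed time or order of readings. The sign of a change is not defined, nor is the way before and after readings are combined when a child has both.

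**The concern.** Within one pair, time and temperature move together. If EE changes between the two readings for another reason (recovery, feeding, lighter sedation), that change is attributed to temperature. In a before-to-fever pair an upward drift adds to the apparent fever effect; in a fever-to-after pair it subtracts. A downward drift does the reverse. The pooled estimate is free of this only if the two kinds of pair balance in number and in gap length, and nothing in the plan secures that balance.

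The result is to be read against 10% of baseline EE per °C, and the conclusion about treating fever or mounting a randomised trial follows from which side it falls on. The expected temperature change is only 0.7°C, so a drift of a few per cent in EE is magnified when expressed per degree. The protocol itself says, under Sample size, that too little is known about the variability of EE over the interval to be measured.

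**Working it through.** **Inputs from the protocol.** Threshold 10% per °C (Hypothesis). SD 10%, one-tailed α 0.05, power 0.80, expected temperature change 0.7°C, 15 children (Sample size).

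**The plan's own figure.** 10/0.7 = 14.3, rounded up to 15. A true effect of 10% per °C over 0.7°C is 7% of EE. With SD 10% per pair, a one-sided paired t-test against zero on 15 pairs has power 0.82. This is the no-drift reference.

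**Assumptions, not in the documents.** D is the drift in EE between the two readings, in %. p is the share of before-to-fever pairs.

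**Bias with equal gaps.** The mean fever-minus-no-fever difference is shifted by pD − (1 − p)D = (2p − 1)D. Per °C the bias is (2p − 1) × D/0.7.

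| D | p = 0 | p = 0.25 | p = 0.5 | p = 0.75 | p = 1 |
|---|---|---|---|---|---|
| 1% | −1.4 | −0.7 | 0 | +0.7 | +1.4 |
| 3% | −4.3 | −2.1 | 0 | +2.1 | +4.3 |
| 5% | −7.1 | −3.6 | 0 | +3.6 | +7.1 |
| 7% | −10.0 | −5.0 | 0 | +5.0 | +10.0 |

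A D of 3% corresponds to 0.75% per hour over four hours (0.75 × 4 = 3).

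**Bias with unequal gaps.** For a drift of r % per hour and gaps g₁ (before to fever) and g₂ (fever to after), the bias is [p·r·g₁ − (1 − p)·r·g₂]/0.7. At p = 0.5 and r = 1:
- gaps of 4 h and 8 h give (2 − 4)/0.7 = −2.9% per °C;
- gaps of 4 h and 12 h give (2 − 6)/0.7 = −5.7% per °C.

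An even mix is therefore not enough when the second gap is open-ended.

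**Effect on the test** (15 pairs, SD 10%, upward D = 3%, one-sided 0.05 against zero).
- No true effect: the false-positive rate is 0.30 if all pairs are before-to-fever, 0.15 at 80%, 0.07 at 60%, and 0.003 if all are fever-to-after.
- True effect of 10% per °C: power falls from 0.82 to 0.43 if all pairs are fever-to-after.

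**Does chronological signing help?** In simulation (true slope 10% per °C, common drift 3% per pair, temperature change about 0.7°C with SD 0.2°C), later-minus-earlier EE was regressed on later-minus-earlier temperature, with an intercept to absorb the drift. The mean slope was 10.0 to 10.1 when both directions occurred. The fever-minus-no-fever ratio averaged 5.3 with all pairs fever-to-after and 12.7 with 80% before-to-fever. With all pairs fever-to-after, the regression slope had a standard error of about 14, so drift and temperature could hardly be separated.

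With elapsed time as the extra term (drift 0.75% per hour), the slope was again about 10 when both directions occurred, with a standard error of 3.6 to 4.8 against about 3.7 for the planned contrast. That contrast itself ranged from 6.7 to 11.6. A pair-direction term raised the standard error to about 12, because direction nearly duplicates the sign of the temperature change.

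**Bracketing.** With equal, independent error variance σ², a single difference has variance 2σ². A febrile reading minus the mean of two equally spaced others has variance (1 + ¼ + ¼)σ² = 1.5σ². The ratio is 0.75, or 0.87 on the SD scale, a 13% reduction. Per °C that gain is gone once the averaged temperature difference falls from 0.7°C to 0.7 × 0.866 = 0.61°C. An example is a before reading 0.7°C below the febrile one with an after reading only about 0.51°C below it (2 × 0.606 − 0.7 = 0.51).

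**The case against.** The strongest reply is that time is not ignored. The before-to-fever gap is capped at four hours unless conditions are unchanged. Stability is checked over the previous hour, recording is continuous where feasible, and the model adjusts for COMFORT score, inotropes and paralysis. This stands, and it rules out saying that the plan takes no account of time. The controls are still partial. The cap covers one kind of pair, the look-back covers the hour before a reading and not the interval between readings, sedation is checked for increases only, and the covariates do not enter the t-test. Nutritional intake is collected but not modelled.

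A reader might infer that drift is simply counted as a fever effect. That does not follow. Its sign differs between the two kinds of pair, so pooling can reduce the bias, and an even mix with equal gaps removes it. With D = 3% and a 60:40 mix the bias is 0.2 × 3/0.7 = 0.9% per °C.

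A reader might also take a range such as 2.9 to 11.4% per °C as the likely error. That range needs an assumed drift of 0.5 to 2% per hour, the full four hours, and every pair running the same way (2/0.7 and 8/0.7). It is a worst case.

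Finally, the Introduction says "We do not know how much energy is used in generating fever by children in the intensive care unit", and the 0.7°C comes from "An analysis of temperature change following over 5000 doses of paracetamol in febrile children". A reader might infer that measuring falls contradicts the aim. It does not: the Introduction goes on to include readings either side of fever, and neither the Aim nor the primary outcome specifies a direction.

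**Conclusion.** The concern holds as a gap in the analysis plan. Two kinds of pair are combined, one of them with an open-ended interval, and neither analysis contains elapsed time or order. If EE drifts and the pairs or gaps are unbalanced, the estimate per °C is biased. The direction of that bias cannot be told from the documents, and neither can its size, because they give no drift rate and no expected mix.

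On an assumed 3% drift with equal gaps, the bias lies between −4.3 and +4.3% per °C, which is up to 43% of the 10% threshold (4.3/10), and is zero at an even mix. It would reach the threshold only with a 7% drift and all pairs in one direction. The model could absorb a common drift if changes were signed chronologically and an intercept kept, but the plan does not say that this will be done. The point is worth acting on because the remedy is cheap; it does not show that the planned estimate will be wrong.

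**What to change.** State the following in the analysis plan before the data are examined.

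1. Define each change in EE and in temperature as later minus earlier. Add elapsed time between the two readings as one term in the multi-level model, at least as a prespecified sensitivity analysis. Do not add a pair-direction term, which is nearly collinear with signed temperature change.
2. In children with both before and after readings, compare febrile EE with the time-weighted average of the two, that is, the value interpolated to the time of the febrile reading. Divide by the febrile temperature minus the same weighted average of the two temperatures. This removes linear drift even when the gaps differ.
3. Report the estimates from rises and from falls side by side, with the number of pairs and the gaps, and without a formal test between them. Keep all pairs in the primary estimate.

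The cost is small. No extra measurements are needed, provided the clock time of each reading is kept. The time term will be imprecise with 15 children and poorly identified if nearly all pairs run one way, and the report should then say so. The 13% reduction in SD from bracketing applies only to three-reading children with equal spacing and independent errors, and can be lost per °C if the after reading is only just below 38°C.
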